5.1. Inclusion criteria

- 1. Ischemic stroke within 72 h after onset, confirmed by MRI or CT;
- 2. Age 35–75 years, inclusive;
- 3. Patients with the first attack or patients with stroke history (modified Rankin Scale score 0-1);
- 4. Clear signs of localization of nervous system, NIHSS score 4 to 22;
- 5. Patient or proxy has signed *Informed Consent Form*.

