7.1.2 Secondary efficacy endpoint

1. Improvement in neurological deficit (proportion of patients with NIHSS ≤1 or NIHSS improved by 4 points or more)

- 2. Improvement in activities of daily living (proportion of patients with BI index \geq 85)
- 3. Disability rate (proportion of patients with mRS score \geq 3 points);
- 4. Continuous changes of mRS scores;
- 5. Incidence of ischemic cerebrovascular disease during follow-up;
- 6. Incidence of combined vascular events during follow-up;

7.2 Safety indicators:

- Adverse event assessment
- Clinical laboratory indicators include blood routine (hemoglobin, red blood cells, white blood cells, platelets), urine routine (urine protein, urine white blood cells, urine red blood cells), serum biochemistry (alanine aminotransferase, aspartate aminotransferase, alkaline phosphatase, glutamine, urea nitrogen, creatinine, total bilirubin, blood glucose, total cholesterol, triglycerides, low-density lipoprotein, high-density lipoprotein).
- Coagulogram: Coagulation 4-item (PT, APTT, TT, FIB)
- 12-lead ECG
- Physical examination

8 Study Process

Refer to Table 1 for details of the study process.

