9.1 Efficacy determination criteria

9.1.1 Primary efficacy assessment

• The proportion of patients with improvement in activities of daily living 90 days after treatment (mRS score ≤1): mRS ≤1 indicates complete or substantial recovery of activities of daily living, representing a favorable prognosis. Comparison of the proportion of patients with favorable prognosis in the treatment group and the control group 90 days after randomization;

9.1.2 Secondary efficacy assessment:

- Improvement in neurological deficit, i.e., the proportion of patients with NIHSS ≤1 or NIHSS improved by 4 points or more: NIHSS score ≤1 or reduction of ≥4 points is considered effective; compare the proportion of effective and ineffective patients and continuous changes of NIHSS in the treatment group and the control group after 90 days of randomized treatment;
- Proportion of patients with BI index ≥85: BI score ≥85 indicates the ability to live
 independently. Compare the proportion of patients able to live independently between
 the treatment group and the control group 90 days of randomized treatment, as well as
 continuous changes in BI scores between the two groups;
- Disability rate, defined as the proportion of patients with an mRS score ≥3: An mRS score ≥3 indicates the inability to live independently. Compare the percentage of disabled patients between the treatment group and the control group 90 days of

randomized treatment:

- Continuous changes in mRS scores: Compare the changes in mRS scores between the treatment group and the control group at different visit points, including baseline, 7 d, discharge, and 90 d;
- Incidence of ischemic cerebrovascular events during the follow-up period: The
 proportion of ischemic stroke or TIA within 90 days of randomized treatment, or
 newly occurring ischemic lesions detected on MRI at the last visit, will be assessed as
 a group or separately;
- Incidence of combined vascular events during the follow-up period: The cumulative
 incidence of newly occurring combined vascular events within 90 days of randomized
 treatment will be assessed as a group or separately;

Definition of combined vascular events: Consist of any type of stroke (ischemic stroke, hemorrhagic stroke), TIA, myocardial infarction, and vascular death.

Vascular death: Hemorrhagic death of any organ or fatal pulmonary embolism.

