BI measures ten basic activities of daily living for patients, including eating, transferring, independent toileting, bathing, walking, or dressing. Based on the difficulty of each task, grade each item on a scale of 0, 5, 10, 15 points to assess the patient. If the patient is unable to complete an activity, the score for each item will be determined by the actual time and amount of assistance required. If the patient requires assistance, even if it's minimal or just supervision, full points cannot be awarded. When the patient cannot meet the specified criteria, it is recorded as 0 points. If a patient scores the maximum points (100 points), they should be able to control bowel movements, feed themselves, get out of bed or chairs, independently bathe, walk at least 50 meters, and go up and down stairs. However, this only means that he can be alone and does not imply that he can live independently (he may be unable to cook or clean the room).

Assessment Guidelines

•This indicator is used to record what the patient has done, rather than what the patient is able to do.

A Randomized, Double-blind, Placebo-controlled, Multicenter Clinical Study of Tongxinluo Capsule in the Treatment of

Ischemic Stroke

·Its primary purpose is to determine the level of independence of the patient in situations where there is no assistance, whether verbal or physical, regardless of how minimal or for what reason.

·In each tested item, the patient is considered not independent when supervision is required.

The patient's performance should be based on the most reliable evidence. Typically derived from the patient's friends, relatives, and nurses, but direct observation and consensus are also crucial.

Generally, the patient's performance in the preceding 24 to 48 hours is crucial, but occasionally it may also be related to a longer duration (such as last week's bowel movements).

Unconscious patients should be scored 0, even if there is no urinary and fecal incontinence.

•Intermediate level implies that the patient's effort exceeds 50%.

If the patient can control urination, an intermediate score implies only occasional urinary incontinence (≤ 1 episode per 24 h).

·Use of assistive tools (such as a cane) is permitted for independence.

Use Guide

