5.2 Secondary effect index

1. Improvement of neurological deficits (ratio of NIHSS≤1 or improve 4 score or more);

Improvement of neurological deficits (ratio of NIHSS≤1 or improve 4 score or more): It is effective for NIHSS≤1 or reducing 4 points or more; compare the ratio of efficacy and inefficacy and the continuous change of NIHSS between treatment group and control group 90 days after random treatment;

2. Improvement of daily life ability (ratio of BI index ≥85);

Ratio of patients with BI index≥85: BI score≥85 indicates the patient with ability of independent living; compare the ratio of patient with ability of independent living and continuous change of BI between treatment group and control group at 90 days after random treatment;

3. Disability rate (ratio of mRS score \geq 3)

mRS≥3 indicates the patient without self-care ability; compare the disability rate between treatment group and control group at 90 days after random treatment;

4. Continuous change of mRS score

Compare change of mRS score at baseline, 7d, discharge day and 90d between treatment group and control group;

5. Incidence of ischemic cerebrovascular diseases during follow-up period;

Ratio of ischemic stroke or TIA within 90 days after random treatment, or ratio of new ischemic focus detected by MRI during the last visit, and take this kind of patients as a group for evaluation or respective evaluation:

6. Incidence of combined vascular events during follow-up period;

Accumulated ratio of patients having newly combined vascular events within 90 days after random treatment;

Definition of combined vascular events: Include any type of stroke (ischemic stroke and hemorrhagic stroke), TIA, myocardial infarction and vascular death.

Vascular death: Hemorrhagic death or fatal pulmonary embolism of any organ.

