6.2.4 Efficiency evaluation

Baseline efficiency: Describe the baseline of each curative index, and comparison between groups should be made in accordance with general condition. Modified Rankin (mRS) score is regarded as ranked data, and should be compared with Wilcoxon rank sum test. NIHSS score should be regarded as quantitative data and ranked data (4-7 points, 8-14 points and 15-22 points) for description and comparison; BI score as quantitative data and enumeration data (<85 points, ≥85 points) for description and comparison.

Primary efficiency indexes:

PP analysis and FAS analysis should be performed at the same time; evaluation on patients with modified Rankin (mRS) score≤1 should be mainly conducted ontaken at day 90 day (PP set) and the time for suspending and drop-out (FAS set). Primary indexes should be compared between the two groups with CMH-γ2 method for controlling central effect.

Superiority test is adopted for primary indexes, and the hypotheses under test are as follows:

$$H_0$$
: $\pi_{\text{treatment group}} - \pi_{\text{control group}} \le 0$

$$H_1: \pi_{\text{treatment group}} - \pi_{\text{control group}} > 0$$

$$\alpha = 0.025_{\text{(one-sided)}}$$

The treatment group is superior to control group, if H0 is rejected under α level, or lower limit of 95% Cl for difference of retention rate between the two groups is higher than 0. Take sensitivity analysis on primary efficiency indexes with modified Rankin (mRS) score≤2 points as the limit.

Other secondary indexes can be statistically analyzed in accordance with methods for primary indexes.

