7.3.4 Secondary effect index - Improvement of daily life ability

Table 7.3.4.1 Inter-group comparison of improvement of daily life ability at 90 days after treatment

		FAS		PPS	
		Treatment		Treatment	
Item	Index	group	Control group	group	Control group
	With ability of				
	independent living				
	n(%)				
	Without ability of				
	independent living				
	n(%)				
Improvement of daily life	N (Missing)				
ability at 90 days after	ν υ,				
treatment					
	Statistics				
	P value				

Note: BI score≥85 points indicates the patient with ability of independent living

Table 7.3.4.2 Continuous change of BI score at 90 days after treatment (FAS)

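### BI ≥85 at Day 90 is a status measure labelled as improvement and as independent living, and its test ignores the baseline BI category the SAP already derives

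*Combined protocol and SAP*

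**What the plan says.** Protocol 7.1.2 lists the endpoint as "Improvement in activities of daily living (proportion of patients with BI index" at or above 85. SAP 5.2 gives it as "Improvement of daily life ability (ratio of BI index ≥85"). Both call it improvement, and both score it by a threshold at Day 90. The synopsis uses a neutral form: the proportion with a BI of 85 or more at 90 days.

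Three places give the threshold a meaning:
- Protocol 9.1.2: "BI score ≥85 indicates the ability to live" independently.
- SAP 5.2: "Ratio of patients with BI index≥85: BI score≥85 indicates the patient with ability of independent living".
- The footnote to SAP Table 7.3.4.1: "Note: BI score≥85 points indicates the patient with ability of independent living".

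Appendix 3 of the protocol describes a patient with the maximum of 100 points and adds: "However, this only means that he can be alone and does not imply that he can live independently".

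Entry severity is set on the NIHSS: "Clear signs of localization of nervous system, NIHSS score 4 to 22" (protocol 5.1). The exclusions add limits on consciousness, swallowing and the limb items. No criterion in either document limits BI.

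Baseline BI is collected at Visit 1 (protocol 8.1). For the baseline comparison, SAP 6.2.4 treats "BI score as quantitative data and enumeration data (<85 points, ≥85 points) for description and comparison", and Table 7.3.1.5 has a row for each category. The same section says that secondary endpoints follow the primary method, which is a CMH test controlling for center.

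**The concern.** A proportion reported as improved should contain patients who improved. Under this rule it also contains patients who were at or above 85 on entry and stayed there, and patients who lost ground but remained at 85. A patient who rises from 0 to 80 is left out. The NIHSS endpoint in the same list does have a change component (a fall of 4 points or more).

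Two things are at stake. The first is wording: the study report would claim improvement and independence from a measure that shows neither by itself. The second is statistical. Patients already above the threshold add a similar amount to both arms' rates, which shrinks the difference in proportions, and a test that ignores baseline BI treats this predictable variation as noise.

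**Working it through.** **1. Can a patient enter at BI ≥85?** Yes. Partial facial paralysis (2) plus severe dysarthria (2) gives an NIHSS of 4. Neither is a BI item, so such a patient could score 100 if able to swallow capsules. The baseline table has a cell for these patients.

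**2. What does the rule count?**

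| Entry BI | Day-90 BI | Counted as improved? |
|---|---|---|
| 85 | 85 | Yes |
| 100 | 85 | Yes |
| 0 | 80 | No |

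**3. The independence reading.** Protocol 9.1.2, SAP 5.2 and the footnote to Table 7.3.4.1 attach independent living to a score of 85. Appendix 3 withholds it at 100. The two statements conflict as written.

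**4. The plan's own figure.** Protocol 4.2 assumes 40% v 47% on the primary, two-sided α 0.05 and 80% power. With p̄ = 0.435,

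n = [1.96·√(2·0.435·0.565) + 0.8416·√(0.40·0.60 + 0.47·0.53)]² / 0.07² = 786.2, so 787 per arm.

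Then 787/0.80 = 983.75, so 984 per arm and 1,968 in total. Both figures reproduce. No rate, effect or power is given for BI ≥85.

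**5. Size of the dilution (all rates assumed).** Let q be the share entering at ≥85. Assume 97% of them are at ≥85 at Day 90 in both arms, and that the others respond at 60% v 67%. Take 787 per arm. Each arm's rate is 0.97q + (1−q)p, so the difference is 7.0·(1−q) points. Power is approximately Φ(difference/SE − 1.96).

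For q = 20%:
- Control rate: 0.2·0.97 + 0.8·0.60 = 0.674. Treatment rate: 0.2·0.97 + 0.8·0.67 = 0.730. Difference: 0.056.
- Ignoring baseline BI, the variance sum is 0.674·0.326 + 0.730·0.270 = 0.417. SE = √(0.417/787) = 0.0230 and z = 2.43, so power is 68%.
- Within baseline strata, the variance sum is 0.2·2·0.97·0.03 + 0.8·(0.60·0.40 + 0.67·0.33) = 0.381. SE = 0.0220 and z = 2.55, so power is 72%.

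The last column below is 0.97q divided by the control rate.

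| q | Difference (points) | Power, baseline BI ignored | Power, adjusted | Control 'improved' patients already ≥85 at entry |
|---|---|---|---|---|
| 5% | 6.7 | 79% | 80% | 8% |
| 10% | 6.3 | 76% | 78% | 15% |
| 20% | 5.6 | 68% | 72% | 29% |

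**6. Allowing for center.** Crossing BI category with 50 centers turns 50 strata into 100. With 2·787 = 1,574 patients, the ≥85 stratum averages 1,574·q/50 = 1.6, 3.1 and 6.3 patients per center. Simulated center-stratified CMH under the same assumptions (6,000 runs) gives about 77/75/67% without BI category and 79/77/71% with it. The gain is about the same size.

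**7. Sensitivity.** Suppose the primary's 40% v 47% applied below 85 and everyone entering at ≥85 stayed there. Power ignoring baseline BI is then 75/71/61%, against 78/76/71% when only patients entering below 85 are analysed. The 1–4 point gain therefore depends on the assumed rates.

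**The case against.** The strongest reply has four parts.

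- *BI change is also compared.* Protocol 9.1.2 and SAP 5.2 both compare continuous change in BI, with Tables 7.3.4.2 and 7.3.4.3 for the FAS and PPS. A patient going from 85 to 100, or from 100 to 85, is captured there. This stands and is a real mitigation. It does not correct the label on the headline proportion. The shell for Table 7.3.4.2 also refers to Table 7.4.2.2, which is diastolic pressure in the safety set.
- *A status endpoint is legitimate.* This stands. The documents use 'improvement' for threshold outcomes generally, including mRS ≤1, and the synopsis already words this endpoint neutrally. The objection here is to the label and the unused covariate, not to a Day-90 status measure.
- *Appendix 3 is mixed.* It also says that the scale's main purpose is to determine the patient's level of independence, and that it indicates opportunities for independent living. That is why reconciling the wording is an acceptable alternative to deleting it.
- *Randomisation balances these patients.* This stands. Allocation is minimised on NIHSS band and thrombolysis, so entrants at ≥85 should be balanced in expectation.

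A reader might also infer that a patient at BI 85 who needs help with bathing and stairs must be mRS ≥3, so that two secondary endpoints contradict each other. The documents do not support that: nothing maps BI to mRS, and the activities listed under mRS level 2 in Appendix 2 name neither bathing nor stairs.

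**Conclusion.** The point holds as one of labelling and precision on a secondary endpoint with no sample size behind it. Three things follow from the text alone: no change is required to count as improved, the planned test of the proportion does not use baseline BI, and the independence reading conflicts with Appendix 3.

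The size does not follow from the text. The share entering at ≥85 and the BI response rates are assumptions. With 5–20% entering at ≥85, response of 60% v 67% below 85 and 97% at or above it, the difference falls from 7.0 to between 6.7 and 5.6 points, and adjustment gains roughly 1–4 power points. Lower response below 85 would make the gain larger.

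Two stronger readings are tempting. A reader might infer that the comparison is biased or its type I error inflated. Neither follows, because the rule is the same in both arms and the diluted difference is still a valid estimate for the status measure. A reader might also infer that the SAP expects many such patients, since it tabulates baseline BI ≥85. An empty table shell allows for the category and says nothing about its size.

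**What to change.** 1. Adjust the BI ≥85 comparison for baseline BI (<85/≥85, or continuous) as well as center. Use a model, or a CMH that tolerates sparse center-by-BI strata. The cost is sparser strata, or a model in place of plain CMH. It is more than one added stratum, because crossing BI category with 50 centers doubles the number of strata.
2. Use the synopsis label, the proportion with BI ≥85 at 90 days, in protocol 7.1.2 and 9.1.2, SAP 5.2 and Table 7.3.4.1. Keep 'improvement' for the BI-change analysis, or for a proportion among patients with baseline BI <85 that is marked as supportive, since it adds another efficacy result. Correct the cross-reference in Table 7.3.4.2.
3. Remove the independent-living interpretation from protocol 9.1.2, SAP 5.2 and Table 7.3.4.1, or reconcile it with Appendix 3.

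Baseline BI is already collected and categorised, so no visits, new data or sample-size change are needed. The cost is wording, one analysis specification and, if the supportive proportion is used, an added table row.

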While Tongxinluo Capsules have been widely utilized in clinical practice and basic research in the field of cerebrovascular diseases, most of its clinical studies are single-center, involve relatively small sample sizes, or are retrospective case-control studies. There is a lack of large-sample, multi-center, and prospective randomized controlled trials. [10][11] To further standardize the study on the clinical efficacy and safety of Tongxinluo in ischemic stroke patients, this study will, based on standardized drug treatment, employ the principles of modern evidence-based medicine to assess Tongxinluo Capsule's effects on the self-care ability (modified Rankin Scale), activities of daily living (Barthel Index score), and the degree of neurological deficit (NIHSS score) in acute and recovery phases of ischemic stroke, and comprehensively evaluate the functional level and quality of life of ischemic stroke patients, thereby assessing the clinical efficacy of early administration of Tongxinluo Capsules in ischemic stroke patients.

4. Overall Design and Arrangement

This study is a randomized, double-blind, placebo Controlled, parallel-group multicenter clinical trial conducted in ischemic stroke patients.

4.1. Randomization phase (Day 0 to Day 90):

Patients will be randomized into the treatment group or the control group at a 1:1 ratio. Patients will receive the study drug in addition to the current standard treatment.

Treatment group: Standard treatment + Tongxinluo Capsules (4 capsules/time, tid, po);

Control group: Standard treatment + Tongxinluo Capsules placebo (4 capsules/time, tid, po);

During the treatment period, the use of other traditional Chinese medicines or proprietary Chinese medicines with similar functional components to those of Tongxinluo Capsules should be avoided.

Patients should visit the hospital on Day 7 after randomization, at discharge (if the hospital stay exceeds 21 days, evaluation will be conducted on Day 21), and on Day 90 for efficacy and safety assessments until the completion of the study.

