Appendix 1: Study Flowchart

Study Stage	Screening/Randomization	Double	e-blind Treatm	ent Period	Follow- up Visit*
Visit	1	2	3	4	5
Days	Day -3 to Day 0	Day 7 ± 2	Discharge*	Day 90 ± 7	
Basic information					
Informed Consent					
Form	•				
General data	•				
Medical history	•				
Physical					
examination	•		•		0
Treatment					
Inclusion/exclusion					
criteria	•				
Allocation of					
random numbers	•				
Distribution of					
study drugs	•				
Recording					
concomitant	•	•	•	•	
medications					
Collection and					
counting of drugs			_		
Determination of					
compliance			_		
Completion status				•	
Inclusion/exclusion					
indicators					
CT or MRI*	•		0	•	
Pregnancy test	•				
Safety indicators					
Blood routine	•		0	•	0
Urine routine	•		0	•	0
Biochemistry	•		0	•	0
Coagulation 4-item	•		0	•	0
12-lead ECG	•		0	•	0
Adverse event					 
assessment					0
Efficacy indicators					
Modified Rankin	•	•	•	•	

score					
NIHSS score	•	•	•	•	
BI index score	•	•	•	•	
Combined vascular					
event			•		
Review					
Review by					
investigator					
Review by CRA	•	•	•	•	•
Review by sub-					
center director					

Note: Inclusion/exclusion indicators: CT or MRI*: For patients who have undergone a head CT or MRI examination during the current illness process at the clinical study unit and within 72 h before enrollment, the report or a copy may be attached to the study medical records and re-examination is not required. The centers participating in the radiology subgroup will perform baseline and final follow-up MRI sequence examinations (T1 + T2 + DWI + FLAIR + MRA + T2*). The baseline examination can be completed either before randomization or within 3 days after randomization.

At discharge*: If the patient's hospital stay exceeds 21 days, this follow-up visit will take place on Day 21. Follow-up visit*: Due to the persistent adverse events or clinically significant laboratory abnormalities or vital sign abnormalities that exist at the end of treatment, the investigator considers it necessary to conduct a follow-up visit to obtain follow-up measurement results. The investigator will conduct follow-up visits based on the specific situation, which may also be done via telephone.

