4.1.2 Overall arrangement

All patients are randomly divided into the treatment group and control group at a ratio of 1:1. The patient receives study drug on the basis of current routine basic therapy.

Treatment group: Basic treatment + Tongxinluo Capsules (4 capsules per time, tid, oral administration)

Control group: Basic treatment + Tongxinluo Placebo Capsules (4 capsules per time, tid, oral administration)

Other traditional Chinese medicine or Chinese patent medicine (the traditional Chinese medicine having similar functional components with Tongxinluo Capsule) is not allowed to take during treatment period.

Follow-up should be made on the 7th day, discharge day (if the hospital stay is longer than 21 days, follow-up should be made on the 21th day) and 90th day after randomization, in order to make effective and safety evaluation until the end of study.

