6.1.1 Full analysis set (FAS)

Full analysis set (FAS) or modified intention-to-treat (ITT): Set of all the patients who underwent randomization, given any treatment, and underwent any posttreatment assessment. When main indexes of curative effect are missing, the set should be supplemented with last observation carried forward (LOCF) on the basis of intention to treat (ITT). Comparability analysis and the missing value of secondary effect indexes don't need data-carry-forward. Take analysis on actual data in FAS.

FAS population is the main population for curative evaluation in this study.

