7.3.6 Secondary effect index – continuous change of mRS score

Table 7.3.6.1 Continuous change of mRS score (FAS)

Item	Index	Treatment group	Control group
	N(Missing)		
Baseline mRS score	Mean(SD)		
	Median		
	Q1,Q3		
	Min, Max		
	Statistics		
	P value		
	N(Missing)		
mRS score at 7 days after treatment	Mean(SD)		
•	Median		
	Q1,Q3		
	Min, Max		
	Statistics		
	P value		
	N(Missing)		
Change of mRS score at 7 days after treatment comparing with baseline	Mean(SD)		
r	Median		
	Q1,Q3		
	Min, Max		
	Statistics		
	P value		
	95%CI		
	Statistics		
	P value		
	N(Missing)		
mRS score at discharge day	Mean(SD)		
5	Median		
	Q1,Q3		
	Min, Max		
	Statistics		
	P值 P value		
	N(Missing)		
Comparison of mRS score at discharge			
day comparing with baseline	,		
	Median		
	Q1,Q3		
	Min, Max		
	Statistics		

Study No.: Document No.:

Item	Index	Treatment group	Control group
	P value		
	95%CI		
	P value		
	N(Missing)		
mRS score at 90 days after treatment	Mean(SD)		
	Median		
	Q1,Q3		
	Min, Max		
	Statistics		
	P value		
	N(Missing)		
Changes of mRS score at 90 days after	er Mean(SD)		
treatment comparing with baseline			
	Median		
	Q1,Q3		
	Min, Max		
	Statistics		
	P value		
	95%CI		
	Statistics		
	P value		

Table 7.3.6.2 Continuous change of mRS score (PPS)

The same as above

7.3.7 Secondary effect index – incidence of ischemic cerebrovascular diseases during follow-up period Table 7.3.7.1 Inter-group comparison of incidence of ischemic stroke within 90 days after treatment

		FAS		PPS	
		Treatment		Treatment	
Item	Index	group	Control group	group	Control group
	With n(%)				
	Without n(%)				
Have ischemic stroke within	N (Missing)				
90 days after treatment					
	Statistics				
	P value				

Table 7.3.7.2 Inter-group comparison of TIA incidence within 90 days after treatment

The same as above

Table 7.3.7.3 Inter-group comparison of ratio of new ischemic focus detected by MRI at last visit

		FAS		PPS	
		Treatment		Treatment	_
Item	Index	group	Control group	group	Control group
	With n(%)				_
	Without n(%)				
New ischemic focu	s detected N (Missing)				
by MRI at the last v	risit				
	Statistics				
	P value				

Table 7.3.7.4 Inter-group comparison of incidence of ischemic cerebrovascular disease during follow-up period

		FAS		PPS	
		Treatment		Treatment	
Item	Index	group	Control group	group	Control group
	With n(%)				
Have ischemic cerebrovascular disease during visit	Without n(%)				
	N (Missing)				
	Statistics				
	P value				

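### mRS is tested between arms at a discharge visit with no fixed day; if length of stay differs by arm, that one secondary contrast is distorted

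*Combined protocol and SAP*

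**What the plan says.** SAP 5.2 item 4 makes the comparison over visits a secondary endpoint: "Compare change of mRS score at baseline, 7d, discharge day and 90d between treatment group and control group". Protocol 9.1.2 plans it for the "treatment group and the control group at different visit points, including baseline, 7 d, discharge, and 90 d".

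The shell in SAP 7.3.6 (Table 7.3.6.1) has a block headed "mRS score at discharge day" with a statistic and a P value. A second block, for change from baseline at discharge, adds a 95% CI.

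The visit is defined in protocol 4.1, protocol Appendix 1 and SAP 4.1.2. Appendix 1 says: "If the patient's hospital stay exceeds 21 days, this follow-up visit will take place on Day 21". Shorter stays are assessed on the day the patient leaves. In the flow charts the other two post-baseline visits are Day 7 ± 2 and Day 90 ± 7; the discharge column has neither a day nor a window.

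On method, SAP 6.2.4 says: "Other secondary indexes can be statistically analyzed in accordance with methods for primary indexes". The primary method is a CMH chi-square test controlling for center. On missing data, SAP 6.1.1 adds that "the missing value of secondary effect indexes don't need data-carry-forward".

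**The concern.** A between-arm test at a visit is like-for-like in time only if both arms are assessed at about the same time after randomization. Day 7 and Day 90 meet that condition; discharge does not. No lower bound is given, so Visit 3 can fall anywhere up to Day 21, even before Visit 2. Because discharge follows randomization, its day can itself respond to treatment.

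The documents do not say what triggers discharge. Protocol Appendix 3 does, however, describe the Barthel Index as reflecting length of hospital stay and as useful for predicting it. A link between functional status and stay is therefore part of the protocol's own account, and the trial aims to improve function.

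If treated patients leave sooner, they are scored earlier on the recovery curve, and part of any benefit is lost from the discharge contrast. If treatment lengthens stay, the distortion runs the other way. Nothing in the SAP would show which has happened: discharge day is not tabulated by arm.

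**Working it through.** **1. The plan's own figure.** The documents give no figure for the discharge contrast. The sample size is needed only for a standard error, so it was reproduced first. Inputs (protocol 4.2, SAP 4.4): 40% versus 47%, two-sided alpha 0.05, power 80%, 20% dropout.

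- n per arm = [1.960 × √(2 × 0.435 × 0.565) + 0.842 × √(0.40 × 0.60 + 0.47 × 0.53)]² / 0.07² = 787 (pooled variance, no continuity correction)
- 787 / (1 − 0.20) = 983.75, so 984 per arm and 1,968 in total. Both stated figures reproduce.

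**2. Simple arithmetic on assumed inputs.** Neither the recovery slope, the difference in stay nor the SD of mRS is in the documents. Assume mRS falls by 0.03 to 0.08 points per day between Days 7 and 21, mean discharge day differs by 1 to 3 days between arms, and the SD is 1.3.

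- Spurious difference = slope × difference in days: 0.03 × 1 = 0.03, up to 0.08 × 3 = 0.24 points
- SE with 984 per arm = 1.3 × √(2/984) = 0.059, so about 0.5 to 4.1 SE
- SE with 787 per arm = 1.3 × √(2/787) = 0.066, so about 0.5 to 3.7 SE

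This applies one slope to both arms, so it isolates the effect of timing alone.

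**3. Simulation on assumed inputs (400,000 per arm).** Latent severity at day t is b − r(1 − exp(−t/τ)), with b ~ N(3.5, 0.7), r ~ N(2.0, 0.7) with a floor of 0.1, and τ = 30 days divided by the recovery multiplier. In the first set of scenarios, stay is independent of recovery: lognormal with median 13 days and log-SD 0.4, held between 3 and 21 days, giving a control mean of 13.5 days. Entries are treatment minus control in change from baseline; negative favors treatment.

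| Scenario | Mean stay (days) | At discharge | At fixed Day 14 |
|---|---|---|---|
| No effect on mRS, stay × 0.8 | −2.4 | +0.105 | 0.000 |
| Recovery × 1.15, stay unchanged | 0.0 | −0.080 | −0.085 |
| Recovery × 1.15, stay × 0.9 | −1.2 | −0.027 | −0.085 |
| Recovery × 1.15, stay × 0.8 | −2.4 | +0.034 | −0.085 |
| Recovery × 1.15, stay × 0.7 | −3.7 | +0.100 | −0.084 |
| Recovery × 1.3, stay × 0.8 | −2.4 | −0.033 | −0.164 |

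In the second set, discharge is triggered by reaching a recovery threshold (severity 2.8, plus about 3 days, with the same limits):

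| Scenario | Mean stay (days) | At discharge | At fixed Day 14 |
|---|---|---|---|
| Recovery × 1.15 | −0.6 | −0.050 | −0.086 |
| Recovery × 1.3 | −1.1 | −0.093 | −0.165 |
| Recovery × 1.5 | −1.7 | −0.142 | −0.261 |

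**4. Steps 2 and 3 agree.** Simulated control patients improve by 0.416 points by Day 7 and 0.746 by Day 14, a slope of (0.746 − 0.416)/7 = 0.047 per day. Multiplied by the 2.4-day difference, that is 0.11, against the simulated 0.105.

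**5. Reading.** In every scenario where stay shortens, the discharge contrast is less favorable to treatment than the Day 14 contrast. The sign turns only where stay shortens by more than the assumed gain in recovery offsets. With stay unchanged, the two contrasts nearly coincide.

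**The case against.** The strongest reply is that function at discharge is an interpretable milestone, so testing it is partly a choice of what to estimate. If treatment affects neither recovery nor stay, randomization keeps the test valid. Both statements stand. But the plan places discharge in a series of time points and gives the reader no discharge day by arm, so a difference in timing could not be told apart from a difference in recovery.

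A reader might infer more than the documents support:

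- **That a drug which speeds discharge would look worse than control.** This does not follow. With discharge triggered by recovery, the simulated benefit shrinks but keeps its sign; reversal needs a larger shortening of stay.
- **That a planned trend is corrupted.** Table 7.3.6.1 lays out separate summaries and tests at each visit. The SAP specifies no trend test and no repeated-measures model.
- **That greater severity in one arm would prolong its stay and reverse the bias.** NIHSS band is a minimization factor, so a systematic difference would have to come from treatment.
- **That the 95% CI in the discharge block is a between-arm interval.** The shell does not label it. The between-arm comparison rests on SAP 5.2 and protocol 9.1.2.
- **That the primary result is biased.** It is assessed at Day 90. Under SAP 6.1.1 a missing primary value is carried forward, so a discharge score could stand in for Day 90, but that is a separate question about LOCF.

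It is also fair that the size rests wholly on assumptions, and that the Day 21 cap compresses differences in stay: a 20% cut from 13.5 days would be 2.7 days uncapped, but came out at 2.4 with the assumed limits.

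**Conclusion.** The point holds for one visit of one secondary endpoint. The plan tests mRS between arms at a post-randomization visit whose day treatment can affect, with no adjustment for that day and no display of it. The distortion depends on a between-arm difference in stay; without one it is negligible. With a shorter treated stay, and mRS improving over time, the benefit is understated relative to a common fixed day and may change sign. The range of 0.03 to 0.24 points illustrates what assumed inputs produce and is not an estimate for this trial. The primary endpoint and the Day 90 comparisons of mRS, NIHSS, BI and disability are not directly affected. This is a worthwhile, inexpensive improvement, not a threat to the main conclusion.

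**What to change.** In SAP 5.2 item 4, Table 7.3.6.1 and protocol 9.1.2, limit the between-arm tests of mRS to Day 7 and Day 90. Present the discharge score descriptively, and add rows giving the actual study day of that assessment by arm. If all visits are to be compared, add a longitudinal model that uses the actual assessment day as time; neither document has such a model now, so it would have to be specified in full.

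The cost is one lost P value at a secondary time point, and a protocol change alongside the SAP change so that the two do not conflict. No new data should be needed: the time-window check in the blind review (protocol 13.3) implies that visit dates are recorded. The synopsis is untouched, since its only secondary mRS endpoint is the 90-day shift analysis.
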